8.1 Definitions

Unanticipated adverse device effect (UADE): Any serious adverse effect on health or safety or any lifethreatening problem or death caused by, or associated with, a device, if that effect, problem, or death was not previously identified in nature, severity, or degree of incidence in the investigational plan or IDE application (including a supplementary plan or application), or any other unanticipated serious problem associated with a device that relates to the rights, safety, or welfare of subjects.

Associated with the investigational device: There is a reasonable possibility that the adverse effect may have been caused by the investigational device.

Life-threatening adverse effect: Any adverse effect that places the subject, in the view of either the investigator or the sponsor, at immediate risk of death from the effect **as it occurred**. It does not include a reaction that, had it occurred in a more severe form, might have caused death.

Serious adverse effect: An adverse effect is considered "serious" if, in the view of either the investigator or the sponsor, it results in any of the following outcomes:

- death
- a life-threatening AE
- inpatient hospitalization or prolongation of existing hospitalization
- a persistent or significant disability/incapacity
- a congenital anomaly/birth defect.

Unanticipated adverse effect: Any adverse effect, the nature, specificity, severity, or frequency of which is not consistent with the risk information in the clinical study protocol or elsewhere in the current IDE application.

8.2 Recording of Adverse Device Effects

All observed or volunteered adverse effects (serious or non-serious) and abnormal test findings, regardless of treatment group, if applicable, or suspected causal relationship to the investigational device or, if

applicable, other study treatment or diagnostic product(s) will be recorded in the subjects' case histories. For all adverse effects, sufficient information will be pursued and/or obtained so as to permit 1) an adequate determination of the outcome of the effect (i.e., whether the effect should be classified as a serious adverse effect) and; 2) an assessment of the causal relationship between the adverse effect and the investigational device or, if applicable, the other study treatment or diagnostic product(s).

Adverse effects or abnormal test findings felt to be associated with the investigational device or, if applicable, other study treatment or diagnostic product(s) will be followed until the effect (or its sequelae) or the abnormal test finding resolves or stabilizes at a level acceptable to the sponsor-investigator.

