4.1 Inclusion Criteria

AD patients will be recruited in person and have to be over 50 years of age and able to give consent. Patients diagnosed with early stages of AD or with MCI will be included in our study. Other more severe symptomatic patients will be eligible to enroll, as long as they have the ability to consent for their participation. Screening is essential and will be performed by our collaborator and neurologist of the study, [name], MD at the Taub Institute of Alzheimer's Disease and Aging at Columbia. After the initial screening we will acquire MRI scans as part of the study and finalize enrollment or exclusion of the patient. Inclusion criteria thus include:

- Age greater than 50 years old.
- Diagnosis of early AD or MCI at minimum. All following criteria must be met:
 - Probable MCI or AD consistent with criteria outlined in (McKhann *et al* 2011, Petersen *et al* 2018).
 - MMSE score between 12 and 26.
 - Modified Hachinski Ischemia Scale (MHIS) score of <= 4
 - Short form Geriatric Depression Scale (GDS) score of ≤ 6 .
 - PET scan confirming amyloid plaque load using Amyvid (¹⁸F-Florbetapir).
- Ability to provide informed consent.

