4.3 Subject Recruitment and Screening

Subjects who have been diagnosed with early AD or MCI, will be identified and informed about our study by our neurologist, [name], or any other trained neurologist. Neurologists will follow the guidelines suggested by the American Academy of Neurology, assessing for functional impairment and behavioral/neuropsychiatric symptoms to establish MCI or AD (Petersen *et al* 2018, McKhann *et al* 2011) according to the following inclusion criteria:

- Probable MCI or AD consistent with criteria outlined in (McKhann *et al* 2011, Petersen *et al* 2018).
- Modified Hachinski Ischemia Scale (MHIS) score of <= 4.
- Mini Mental State Exam (MMSE) scores of 12-26.
- Short form Geriatric Depression Scale (GDS) score of <= 6.
- PET scan confirming amyloid plaque load.

Should the patient agree to participate, a written permission will be asked to allow the treating physician to forward their name and contact information to the research investigators. The patients may also be given the contact information for the researchers, so that they may contact them if they are interested in participating. [name] or any other participating neurologist will document in the subject's medical record that permission has been obtained for the study team to contact the subject about enrollment in this study. [name] will enroll patients with moderate AD (MMSE scores: 12-18) who are not subject to higher risk of adverse effects due to mental impairment. PET scans are routinely conducted to confirm AD and are not expected to affect the safety of the FUS treatment.

Patients will be screened using the iNYP database on a password-protected computer with a secure ethernet connection. Discussion with subjects regarding research participation will take place in a private area (i.e., a patient exam room). All procedures related to the research study will also be carried out in a private room. The data acquired during research procedures will be anonymized and encrypted, and immediately removed from the ultrasound systems and transferred to the secure endpoint using an encrypted portable hard drive. After the transfer is complete, the imaging data will also be removed from the portable drive. Focus groups will not be used for this study. Subject privacy will be protected as described in attached HIPAA form.

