In the second visit, BBB opening will be attempted in a designated facility in the hospital using the described FUS system. First, a baseline cavitation signal will be obtained prior to microbubble injection. Then, an intravenous injection of Definity microbubbles under the FDA guidelines will be administered as a bolus or via a syringe pump and the cavitation signal will be monitored and recorded during sonication at acoustic parameters well below the FDA safety limit (MI = 0.4). In this EFS, we will target the prefrontal cortex (PFC). PFC has been shown to be affected by AD pathology, leading to deficits in attention, spatial memory and planned movements. Although we do not aim to treat AD in this EFS, PFC was selected as the targeted structure due to its relevance to this condition, its size and ease of targeting with our singleelement transducer. A follow-up MRI (with and without contrast) will be acquired the same day after BBB opening to ensure treatment safety and efficacy. Finally, two blood samples will be collected before and after treatment through an intravenous catheter or a finger prick. Blood analysis will be performed to test whether there are acute changes in the blood test results due to the FUS application. Based on our animal studies, there is an acute increase in reticulocytes, platelets and eosinophils after FUS treatment, possibly due to the BBB restoration process. Blood samples will be used to test whether these changes in blood chemistry occur also in humans. Blood samples will be stored and analyzed to detect potential changes in Alzheimer's Disease biomarkers and other compounds that may exit the brain parenchyma because of the blood-brain barrier opening (e.g. exosomes). All time points will be compared to baseline acquired during screening.

6.3 Visit 3

A follow-up MRI (with and without contrast) will be performed three days (± 1 day) after treatment to confirm BBB closure and to assess safety. A blood sample will be collected through an intravenous catheter or a finger prick, to test for short-term changes in blood chemistry and cell count.

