6.4 Visit 4/5

Follow-up visits will be required three weeks (± 1 week) and three months (± 2 weeks) after treatment to assess long-term safety, amyloid plaque load and cognitive function through behavioral tests. Two follow-up PET/CT scan using Amyvid (¹⁸F-Florbetapir) will be performed; one 3 weeks (± 1 week) post-FUS and one 3 months (± 2 weeks) post-FUS, to test for potential reduction in the amyloid plaque load. A blood sample will be also collected through an intravenous catheter or a finger prick, to test for long-term changes in blood chemistry and cell count. One follow-up visit following a single FUS treatment was deemed sufficient by the attending neurologist.

7 Statistical Plan

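### Symptoms that start after the subject leaves the site are likely to be under-recorded, because section 8.2 provides for no questioning and no informant in patients with MMSE scores as low as 12

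*Combined protocol and SAP*

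**What the plan says.** Section 8.2 requires that "All observed or volunteered adverse effects (serious or non-serious) and abnormal test findings" be entered in the case histories, whatever their suspected cause. That gives three routes into the record: what staff notice, what the subject brings up, and what a test shows. No question to the subject is among them.

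Section 4.1 admits subjects with "MMSE score between 12 and 26" and requires "Ability to provide informed consent". Section 4.3 adds that the neurologist "will enroll patients with moderate AD (MMSE scores: 12-18) who are not subject to higher risk of adverse effects due to mental impairment". Neither section mentions a study partner or informant.

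The visits are described in section 6:

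- Visit 2 has the sonication, an MRI the same day, and blood samples before and after.
- Visit 3 has a blood sample and an MRI that "will be performed three days (± 1 day) after treatment to confirm BBB closure and to assess safety".
- For Visits 4 and 5, section 6.4 states: "Follow-up visits will be required three weeks (± 1 week) and three months (± 2 weeks) after treatment to assess long-term safety". Plaque load and cognitive function are assessed too, with PET/CT and a blood sample.

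No visit lists a symptom enquiry. Section 9.2 names subject diaries and checklists, but only as generic examples of source documents.

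Section 3.4 bases the primary safety assessment on MRI and neurocognitive tests. Sections 8.6 and 8.6.1 provide for a clinician at the treatment session, a neurologist's evaluation at three months, and cognitive testing with unnamed instruments. The table in section 8.5 lists the potential adverse effects by severity.

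**The concern.** A volunteered report needs the subject to notice a symptom, remember it until the next contact, and raise it unprompted. Every subject here has a condition that impairs memory, and moderate AD is expressly admitted. Several effects that the protocol itself anticipates leave no trace on a scan or in a blood sample once they have passed.

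Safety is half of the study's stated purpose, and section 8.6.1 concedes that long-term effects in the human brain have not been investigated. A missed report can only lower the count. With six subjects, an absence of recorded symptoms is already weak evidence, and incomplete capture weakens it further. A symptom that nobody asked about at the time cannot be recovered afterwards.

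**Working it through.** The plan gives no figure for how completely adverse effects are captured, so there is none to reproduce. The six subjects (sections 3.1, 6 and 7.1) are taken as given.

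**1. Effects that depend on the subject's report.** The section 8.5 table has 4 severe, 4 moderate and 3 mild items: 4 + 4 + 3 = 11. Headache, nausea, dizziness, emesis and skull heating are known largely from the subject. That is 5 of 11, or 5 of the 7 moderate and mild items. Skull heating arises during sonication, under supervision, which leaves four of the five that can plausibly start at home.

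**2. Time between contacts.** The inputs are the windows in sections 6.3 and 6.4, with three months read as 13 weeks (91 days).

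| Contact | Nominal day | Window |
|---|---|---|
| Visit 3 | 3 | 2 to 4 |
| Visit 4 | 21 | 14 to 28 |
| Visit 5 | 91 | 77 to 105 |

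- Visit 3 to Visit 4: nominal 21 − 3 = 18 days; shortest 14 − 4 = 10; longest 28 − 2 = 26.
- Visit 4 to Visit 5: nominal 91 − 21 = 70 days; shortest 77 − 28 = 49; longest 105 − 14 = 91.

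**3. Illustration of the effect on a count in six subjects.** Let *p* be the true risk of a symptom and *s* the share of true cases that reach the record. With independent subjects, P(none recorded) = (1 − *p* × *s*)^6. Both *p* and *s* are assumptions; the protocol supplies neither.

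| Assumed true risk | Full capture | 75% captured | 50% captured |
|---|---|---|---|
| 10% | 0.90^6 = 53% | 0.925^6 = 63% | 0.95^6 = 74% |
| 20% | 0.80^6 = 26% | 0.85^6 = 38% | 0.90^6 = 53% |
| 30% | 0.70^6 = 12% | 0.775^6 = 22% | 0.85^6 = 38% |

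The same can be read from the other side. If no case is recorded in six, the one-sided 95% upper bound on the recorded rate is 1 − 0.05^(1/6) = 39.3%. The bound on the true rate is this divided by *s*: 39.3 / 0.75 = 52.4%, and 39.3 / 0.5 = 78.6%.

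**4. What *s* stands for.** It is an average over two settings. If a share *f* of cases arises on site and all of those are seen, and a share *r* of the remainder is reported, then *s* = *f* + (1 − *f*) × *r*. A value of 50% is then possible only if *f* is at most 50%. For symptoms that arise mainly under supervision, the full-capture column is the closer one.

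**The case against.** The strongest case against is that the safety assessment does not rest on volunteered reports. Section 3.4 puts it on MRI and neurocognitive tests, and section 8.2 itself covers abnormal test findings. MRI is done on the treatment day and at day 3, and blood is taken at every stage. The acute effects in the section 8.5 table would be expected mostly around the sonication, when a clinician is present, and the next contact follows within 2 to 4 days with safety as a stated purpose. The late visits also have a safety purpose, with a neurologist's evaluation at three months. How these assessments are done is unspecified, which is not the same as passive, and what a clinician finds on examination counts as observed. Section 4.3 qualifies the entry of moderate AD, and every subject must be able to consent.

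Much of this stands. A reader might infer that safety as a whole is biased toward looking clean, or that nothing enters the record unless somebody notices or mentions it. The documents do not support either reading: imaging, laboratory and cognitive findings and directly supervised effects enter without recall. A reader might also infer that one or two unreported symptoms would change the study's conclusion. No success rule, analysis or stopping threshold counts mild or moderate symptoms, and the pause rule in section 8.5 concerns serious events. The longest gaps, 26 and 91 days, are also extremes of the windows.

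What the objection does not remove is the gap for symptoms that start at home. Scans and blood tests do not show a headache or vomiting that has resolved. No MRI is scheduled after day 3, and the only stated neurologist's evaluation after treatment is at three months. The qualifier in section 4.3 concerns the risk of having an adverse effect, not the ability to report one. Capacity to consent does not establish recall over weeks.

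**Conclusion.** The point holds for a limited class of events: symptomatic, self-reported effects that arise after the subject has left the site. These are likely to be under-ascertained, and the error runs one way, toward a lower count. Imaging, laboratory and cognitive safety results are not affected.

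The size cannot be derived from the documents. The rise from 12% to 22% or 38% in the chance of an empty record rests on an assumed true risk of 30% and assumed capture of 75% or 50%. It shows the direction and the sensitivity; it is not an estimate. The absence of an informant and of symptom questioning is established only for the available text, which does not include the consent form.

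The change should be made, because it is cheap. Without it, the symptom data from the late visits could not support a statement that a symptom did not occur.

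**What to change.** - In section 8.2, extend the rule to effects that are *observed, volunteered or elicited*, and keep abnormal test findings.
- At Visits 2 to 5 in section 6, ask a standard open question first, then the symptom items already in the section 8.5 table. Put both to the subject and, where one is available, to an accompanying caregiver.
- At Visit 2, record the same items before sonication, so that pre-existing symptoms are not counted as new.
- Record the source of each report (observed, volunteered, elicited from the subject, or given by the caregiver), and tabulate symptomatic effects by source.

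The cost is a one-page checklist at visits already scheduled, with no added procedure or staff. The downside is that more mild events will be recorded than in studies that rely on volunteered reports. The tabulation by source keeps such comparisons possible.

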8.3 Reporting of Adverse Device Effects and Unanticipated Problems

8.3.1 Investigator reporting: Notifying the study sponsor

N/A

8.3.2 Investigator reporting: *Notifying the IRB*

ALL unanticipated adverse device events will be reported immediately and no later than within 2 business days to the IRB committee, regardless of seriousness or severity. Unanticipated problems involving risks to subjects and others will be recorded and reported to IRB within 5 business days. Expected or unrelated adverse effects and potential protocol violations will be recorded and reported in our annual progress report.

Any suspension or terminations of IRB approval will be reported to NIMH no later than within **3 business days of receipt**. Unanticipated adverse effects or serious adverse events will be reported to NIMH no later than within **10 business days** of the study team becoming aware of the event.

8.4 Unblinding Procedures

N/A

8.5 Stopping Rules

Redundant safety features have been added to the hardware of the device, as grounding for the transducer, safety switch for the amplifier and function generator. Additionally, we will incorporate safety valves in our software. For any signs showing safety risk including high cavitation dose in the acoustic monitoring or unstable vital signs, the device can be stopped from the computer user interface and/or an emergency stop button. Treatment will be stopped in the case of any reaction of the subject to the ultrasound exposure or microbubble infusion. Pulse oximetry will be used during MRI scans to mitigate the risk of anaphylactic reaction to MRI contrast agents. Potential adverse effects have been grouped according to their severity in the following table:

Severity	Adverse effect			
Severe	Local hemorrhage	Edema	Intracranial infection	Status epilepticus
Moderate	Emesis	Dizziness	Allergic reaction	Nausea
Mild	Skull heating	Injection site bruising	Headache	

The investigation will be paused and the relevant authorities will be notified in case of any death, life threatening event, or any other serious adverse event described in the table above (including disability or clinically significant manifestation of local hemorrhage or edema) due to the procedure. An episode of status epilepticus during treatment will terminate the session immediately.

If the selected ultrasound settings (i.e., MI of 0.4) do not successfully open the BBB in 3 subjects, FDA will be contacted via a submission of an IDE supplement, to discuss revising the protocol's focused ultrasound parameters or increase the number of subjects.

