4.2 Exclusion Criteria

Exclusion criteria include surgeries and other pathologies not associated with AD, as outlined in the following list:

- Contraindication for MRI.
- Contra-indication history or hypersensitivity to MRI contrast agents (e.g., Dotarem) or microbubbles (e.g., Definity).
- Prior brain surgery, including deep brain stimulation.
- Metallic implants.
- Moderate or severe uncontrolled hypertension.
- Abnormal coagulation profile, e.g. hemophilia A or B.
- Coagulopathy or under anticoagulant therapy.
- History of stroke or cardiovascular disease.
- Active gingivitis, herpes simplex, hepatitis, tuberculosis, and minor skin or respiratory infections.
- History of seizure disorder.
- History of asthma or allergies to food or medication with significant symptoms in past 3 years.
- Severe brain atrophy.
- Inability to comply with the procedures of the protocol, including follow-up MRI scans.
- Pregnancy or lactation.
- Impaired renal function with estimated glomerular filtration rate (eGFR) <30 mL/min/1.73m² provided by a standard blood test 2-4 weeks prior to the ultrasound treatment.
- Active infection/inflammation.
- Acute or chronic hemorrhages, i.e. > 4 lobar microbleeds, and no siderosis or macrohemorrhages.
- Tumors or space occupying lesions.
- Meningeal enhancements.
- Intracranial hypotension.

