5.5 Prior and Concomitant Therapy

Although BBB opening is reversible and transient, it may lead to unintended diffusion of pharmaceutical molecules into the brain parenchyma. To avoid such potential effects, non-critical medications will be withheld prior to treatment and until closure of the BBB is confirmed (at least 24 hours before and after the procedure). For critical medications, medication withholding will be judged based on the subject's diagnosis, condition, and medication type.

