8.6 Medical Monitoring

Medical monitoring will be performed by the neurologist of this study, [name], MD at the Taub Institute of Alzheimer's Disease and Aging at Columbia. [name] or any other trained radiologist will be present during the trial and will assess the subject's clinical status during therapy. In the case of an allergic or any other reaction (e.g. status epilepticus) to the therapy, the study will be immediately discontinued. Resuscitation equipment will be readily available in the study room, in case of a serious adverse event.

Subjects will be monitored with follow-up MRI scans to confirm BBB opening and closing and PET scans to estimate amyloid plaque load. Should the MRI or PET brain scans of this study have incidental findings (e.g. brain tumor, subarachnoid hemorrhage, or structural abnormality) the subject will be immediately withdrawn from the study and directed for clinical care. MRI scans will be examined by [name], who is a certified in Diagnostic Radiology and is the Section Chief of Neuroradiology. MRI scan examination by [name] will occur as soon as possible but no later than two weeks following receipt of the image.

If there are any incidental findings deemed by the clinical-investigator to be "life-threatening" or "important but not severe", both the subject and the subject's personal primary care physician will be notified. Communication may be initially verbal, followed by a formal written communication. The significance of the incidental finding will be determined by the clinical-investigator and communicated to the subject accordingly. Incidental findings of clinical significance and the management of such findings should be documented in the research records of this study.

At the time of a continuing review, if incidental findings were noted during the previous approval period, the principal investigator of this study will provide the IRB with the following information: the number of required review images, a list of the subject study numbers, the type of scan, the date of the scan, a description of the incidental finding of clinical significance, the date of communication with the subject and the outcome, if known.

If the participants expressed severe depression or suicidal ideation in the course of their visit, the subject will be urgently assessed by the study clinician and appropriate referrals will be made. In addition, we will exclude the participant from the study.

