8.6.1 Data Monitoring Committee (if applicable)

The safety of the BBB opening using ultrasound and microbubbles has been confirmed by previous nonhuman primates studies, which revealed no adverse effects, permanent damage, or behavioral change following repeated treatments using low-intensity ultrasound and clinically-relevant microbubble doses. Ongoing clinical trials using this technique have not reported any acute adverse effect in either of the participants. However, long-term effects in the human brain have not been investigated to date.

To ensure the long-term safety in our study, the investigators will monitor and collect the data for processing and analysis while [name] will be present to assess the safety of the patient during FUS application. [name] will be present during the trial and will assess the subject's clinical status during therapy. In the case of an allergic or any other reaction to the therapy, the study will be immediately discontinued. Resuscitation equipment will be readily available in the study room, in case of a serious adverse event. Subjects will be monitored with follow-up MRI scans to confirm BBB opening and closing. BBB opening will be confirmed with an MRI scan immediately after the ultrasound treatment, while BBB closing will be confirmed three days later. Additional clinical evaluation will be performed by [name] or any other trained neurologist 3 months after the ultrasound treatment. Should the MRI brain scans of this study have incidental findings (e.g. brain tumor or potential structural abnormality) the subject will be immediately withdrawn from the study and directed for clinical care. Incidental findings will be communicated with both the subject and the subject's personal primary care physician.

Cognitive function will be assessed by [name] using appropriate tests before, during, and after the treatment.

9 Data Handling and Record Keeping

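### The protocol text lets the next subject be sonicated before the previous subject's same-day and day-3 safety MRIs have been read

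*Combined protocol and SAP*

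**What the plan says.** Six subjects each receive one sonication of the prefrontal cortex at MI 0.4 (3.1, 5.2, 6.2). Each has two post-treatment MRIs with a stated safety purpose. The first (6.2) "will be acquired the same day after BBB opening to ensure treatment safety and efficacy". The second (6.3) is done "three days (± 1 day) after treatment to confirm BBB closure and to assess safety". Section 3.1 gives both scans a safety role as well.

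The deadline for the neuroradiologist's examination of MRI scans is in 8.6: it "will occur as soon as possible but no later than two weeks following receipt of the image". That sentence closes a paragraph that also deals with incidental findings, but it is worded for MRI scans in general. No separate, faster safety read is given.

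The pause rule in 8.5 begins "The investigation will be paused and the relevant authorities will be notified in case of any death, life threatening event" and goes on to other serious events from its severity table that are due to the procedure, including "disability or clinically significant manifestation of local hemorrhage or edema". The table itself lists local hemorrhage and edema in the severe row without that qualifier.

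Two other places bear on how soon the day-3 scan is looked at. Section 5.5 says "non-critical medications will be withheld prior to treatment and until closure of the BBB is confirmed", and 8.6.1 says "BBB closing will be confirmed three days later".

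Sections 3.1, 5.3, 6, 8.5, 8.6, 8.6.1 and 10.1 contain no minimum interval between subjects, no sentinel subject and no scan review that must precede the next treatment.

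**The concern.** This study tests the initial safety of a newly built system in a small cohort (2.1), and MRI is one of the two named tools of the primary safety endpoint (3.4). Reactions during the session are covered by the immediate stops in 8.5, 8.6 and 8.6.1, and a symptomatic later event could be reported clinically. The main uncovered case is a lesion without symptoms that first appears on the day-3 scan. If that scan is unread when the next subject arrives, the pause rule has nothing to act on, and the next subject is treated at the same setting.

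A second, related gap is what happens once such a lesion is read. The 8.5 wording does not settle whether a silent hemorrhage or edema pauses the study. Events first seen at 3 weeks or 3 months are outside this point.

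**Working it through.** The protocol gives no figure for spacing or exposure, so there is none to reproduce. The check is a day count.

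**Inputs from the protocol**
- 6 subjects, so 5 come after the first (3.1, 6).
- Same-day MRI on day 0 (6.2); day-3 MRI on day 2 to 4 (6.3).
- Read limit of 14 days after receipt (8.6).

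**Assumptions**
- The image is received on the day of the scan.
- Subjects are treated every p days, with p = 7, 14 or 21. The protocol states no pace.

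**Formula.** The first subject is treated on day 0, the others on days p, 2p, …, 5p. The result is known on day T = scan day + read lag. Exposure is the number of treatment days earlier than T.

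**Day-3 MRI**
- Read lag 0 to 3 days: T runs from 2 + 0 = 2 to 4 + 3 = 7. No treatment day falls before day 7 at p = 7, 14 or 21, so the count is 0.
- Day-4 scan read 4 calendar days later, across a weekend: T = 4 + 4 = 8. At p = 7 one subject (day 7) precedes it; at p = 14 or 21, none.
- Read at the two-week limit: T = 2 + 14 = 16 to 4 + 14 = 18. At p = 7 two subjects precede it (days 7 and 14); at p = 14 one (day 14); at p = 21 none.

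**Same-day MRI at the two-week limit**
- T = 0 + 14 = 14. At p = 7 one subject precedes it (day 7); at p = 14 or 21, none.

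**Extreme pace.** At one subject per day, which nothing in the protocol supports, the day-3 count is 1 to 3 with same-day reads (T = 2 to 4) and 5 at the two-week limit.

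**The pause wording.** Section 8.1 defines a serious effect by outcome: death, threat to life, hospitalization, disability or birth defect. A silent lesion meets none of these, and the 8.5 parenthesis speaks of clinically significant manifestation. Against that, the parenthesis is introduced as an inclusion, not a limit, and the table places any local hemorrhage or edema in the severe row. Both readings are open.

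**The case against.** The strongest case is that the two-week scenario is unlikely. Two weeks is a ceiling, and the stated aim is to read as soon as possible. The sentence sits among text on incidental findings and may be meant as a backstop for those. The day-3 scan has an express safety purpose. Medication is withheld until closure is confirmed, so a two-week wait would keep non-critical drugs withheld for over two weeks. Screening needs amyloid PET, a planning MRI, renal testing and individual skull simulations. These steps can overlap between subjects, but they may slow accrual enough to remove the exposure. Section 8.2 has abnormal findings recorded and assessed for causality, and 8.3.2 requires unanticipated device events to reach the IRB within 2 business days.

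Much of this stands, and it rules out three stronger readings that a reader might infer:
- That two weeks is the planned turnaround. Section 8.6 does not say so.
- That the day-3 scan is only a check of closure. Sections 3.1 and 6.3 say otherwise.
- That a silent lesion would not pause the study. Section 8.5 is ambiguous, and its table can be read to cover it.

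What does not fall is the absence of a rule. An early look under 5.5 governs the same subject's medication and sets no condition for the next subject. Recording and reporting duties start only once a finding is known. The monitoring plan cited in 10.1 could set spacing but was not available.

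**Conclusion.** The point holds for the protocol text: nothing makes one subject's sonication wait for another's safety MRI to be read, and the only stated read limit is long enough for this to matter at a plausible pace. The exposure is 0 to 2 later subjects at one per week, 0 to 1 at one per two weeks, and 0 at one per three weeks. The upper figures need the full two-week limit to be used. These counts rest on assumed paces and on receipt of the image on the scan day. The ambiguity in 8.5 about silent hemorrhage or edema is a separate weakness in the same rule. Neither shows that later subjects would in fact be exposed. Both leave their protection to scheduling or to a document outside the protocol, in a study where the correction is cheap, so the text should be changed.

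**What to change.** Add two or three sentences to 8.5 and section 6:
- The next subject's Visit 2 takes place only after the existing neuroradiologist has read the previous subject's same-day and day-3 MRIs for safety. The target is 1 to 2 working days, replacing the two-week limit for these scans.
- Any hemorrhage or edema that is new since the Visit 1 MRI, symptomatic or not, holds the next treatment until the medical monitor promptly documents a decision to continue or pause.

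The Visit 1 comparison matters because the exclusion in 4.2 ("Acute or chronic hemorrhages, i.e. > 4 lobar microbleeds") can be read as allowing up to 4 lobar microbleeds at entry. If the monitoring plan already contains such a rule, citing it in 8.5 would do.

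**Cost.** No added scans or subjects. The protocol does not show that the reader can report in 1 to 2 working days, so that is an assumption. With day-4 scans and reads in 2 working days (2 to 4 calendar days), each hold lasts 4 + 2 = 6 to 4 + 4 = 8 days, and there are five holds:
- Flexible treatment days: 5 × max(0, 6 − 7) = 0 to 5 × (8 − 7) = 5 days in total beyond a weekly schedule.
- Fixed weekly slots, every hold missing one: 5 × (14 − 7) = 35 days.
- Three-week spacing: none, even with two-week reads, since 4 + 14 = 18 is less than 21.
- If reads still took two weeks, with flexible days: 5 × (18 − 7) = 55 days beyond weekly.

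An inconsequential or unrelated lesion could also cause a hold, which is why the medical monitor's decision should be prompt.
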